#### Section C-2.2 Incidence rate of clinically relevant anemia for adolescence

Table C-2.2.1 Incidence rate of clinically relevant anemia for adolescence\*, AT population, Complete cohort

	DNG		OAED		NAED			Ex-use	Ex-use Allocation unknown	
		GnRH-a	Danazol	All OAED	СНС	Other progestin	All NAED			
Number of women years	xx	xx	xx	xx	xx	XX	xx	xx	xx	xx
Confirmed anemia	xx	xx	XX	xx	XX	xx	xx	xx	xx	xx
IR** (95% CI)	xx.x (xx.x-x.x)	xx.x (xx.x-x.x)	xx.x (xx.x-x.x)	xx.x (xx.x-x.x)	xx.x (xx.x-x.x)					
Thereof										
Treated with iron	xx	xx	xx	xx	XX	xx	XX	xx	xx	XX
tablets	xx.x (xx.x-x.x)	xx.x (xx.x-x.x)	xx.x (xx.x–x.x)	xx.x (xx.x-x.x)	xx.x (xx.x-x.x)	xx.x (xx.x-x.x)	xx.x (xx.x-x.x)	xx.x (xx.x-x.x)	xx.x (xx.x–x.x)	xx.x (xx.x–x.x)
Treated with iron	xx	xx	xx	xx	xx	XX	XX	XX	xx	XX
infusions/injections	xx.x (xx.x-x.x)	xx.x (xx.x-x.x)	xx.x (xx.x-x.x)	xx.x (xx.x-x.x)	xx.x (xx.x-x.x)					
Treated with blood	xx	xx	xx	xx	xx	XX	XX	xx	xx	xx
transfusions	xx.x (xx.x-x.x)	xx.x (xx.x-x.x)	xx.x (xx.x–x.x)	xx.x (xx.x-x.x)	xx.x (xx.x–x.x)	xx.x (xx.x-x.x)	xx.x (xx.x-x.x)	xx.x (xx.x-x.x)	xx.x (xx.x-x.x)	xx.x (xx.x–x.x)

Note: \* Adolescent at study entry.

Note: \*\* Incidence rate is shown per 10^4 women years.

Table C-2.2.2	Incidence rate of clinically relevant anemia for adolescence*, AT population, Starter
Table C-2.2.3	Incidence rate of clinically relevant anemia for adolescence*, AT population, Switcher
Table C-2.2.4	Incidence rate of clinically relevant anemia for adolescence*, AT population, Restarter
Table C-2.2.5	Incidence rate of clinically relevant anemia for adolescence*, AT population, Diagnosis confirmed by surgery
Table C-2.2.6	$Incidence\ rate\ of\ clinically\ relevant\ anemia\ for\ adolescence^*,\ AT\ population,\ Diagnosis\ based\ on\ clinical\ symptoms$
Table C-2.2.7	Incidence rate of clinically relevant of anemia for adolescence*, AT population, Germany
Table C-2.2.8	Incidence rate of clinically relevant of anemia for adolescence*, AT population, Poland
Table C-2.2.9	Incidence rate of clinically relevant anemia for adolescence*, AT population, Hungary
Table C-2.2.10	Incidence rate of clinically relevant anemia for adolescence*, AT population, Switzerland
Table C-2.2.11	Incidence rate of clinically relevant anemia for adolescence*, AT population, Russia
Table C-2.2.12	Incidence rate of clinically relevant anemia for adolescence*, AT population, Ukraine

Supporting document SOP BMT 01.09 – Doc 5002.02 – Effective date 21.03.2017

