#### Secondary objectives are:

- To characterize the baseline risk of users of the individual formulations (lifetime history of co-morbidity, risk markers, co-medication, socio-demographic and lifestyle data).
- To analyze the drug utilization pattern of DNG and other endometriosis treatments in a study population that is representative for typical use of the individual preparations under routine medical conditions.
- To investigate the risks of short and long-term use of DNG and of established endometriosis treatments in adolescent women.

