#### 3. Study Design

This is a large, prospective, controlled, non-interventional, long-term cohort study which follows two cohorts, users of DNG and users of other medications used for the treatment of endometriosis. The cohorts consist of new users (starter and restarter) or switcher of a hormonal endometriosis treatment. A "non-interference" approach will be used to provide standardized, comprehensive, reliable information on endometriosis treatment patterns.

A follow-up assessment for each woman is scheduled 6, 12, 24, 36 and depending on the date of enrollment 48, 60, 72 and 84 months after baseline. Women will be followed-up for at least 2 years. Women recruited in the early phase of the study will be followed-up until study endpoint [max. 7 years]. By means of these contacts, almost all relevant clinical outcomes will be captured.

However, during the first year of the study, less than 15% of the planned recruitment target within that time frame was achieved (i.e. 1,191 women were recruited rather than the anticipated 8,334 women). As a consequence, the overall recruitment phase was longer (and therefore the observation time was less) than we had expected. In order to achieve the envisaged total observation time of 84,000 women years, the follow-up period will be prolonged by one year (until end of QII 2018).

All clinically relevant serious adverse events will be verified by ZEG through contact with the relevant physicians and by reviewing pertinent source documentation. A standard algorithm will be used to classify 'clinically relevant depression' and 'medically treated anemia' as 'confirmed' or 'not confirmed'. At the end of the study, this classification will be verified by blinded independent adjudication

treatment with GnRH, an estrogen and/or a progestogen (add-back therapy) will be considered as a single treatment regimen. In cases where add-back therapy is used the predefined end-point is the cessation of the add-back therapy.

 Users of non-approved hormonal medications prescribed for endometriosis treatment are additionally followed up and included in the analysis.

 First ever user of EMT

 EMT use after intake break (>= 4 weeks)

 Switching from another EMT

 According Study Protocol, Amendment of September 30, 2017

Supporting document SOP BMT 01.09 - Doc 5002.02 - Effective date 21.03.2017

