#### 5.1 Analysis sets

There are no specific inclusion or exclusion criteria. However, women with a language barrier, a non-hormonal or not newly prescribed baseline medication or women who are pregnant at study enrollment will be excluded from the analysis. The final analyses will include both an "as treated" (AT) and an "intention-to-treat" (ITT) analysis. All women who are not excluded from the analysis will be assigned to the ITT and AT population at baseline. Only women with follow up information will be considered for longitudinal analysis (e.g. distribution of outcomes over time, incidence rates, regression). Women who never started their prescribed baseline medication will be considered in the ITT analysis, but excluded from the AT analysis. The safety conclusions of the study will be based on the AT analysis.

Supporting document SOP BMT 01.09 – Doc 5002.02 – Effective date 21.03.2017

This study follows three cohorts: users of Visanne (DNG), users of other medication approved for the treatment of endometriosis (OAED) and users of non-approved hormonal medications prescribed for endometriosis treatment or those approved only in some participating countries (NAED).

Distribution of women, population characteristics (baseline and follow up) as well as clinical outcomes will be presented for the following cohorts and sub-categories.

Cohort Sub-category for presentation	
DNG	Complete cohort
OAED	GnRH-a, Danazol, complete cohort
NAED	Combined hormonal contraceptives, other progestins, complete

The cohorts consist of new users (starter and restarter) or switcher of a hormonal endometriosis treatment. For the primary analysis, outcomes of interest or adverse events will be assigned to the treatment at the time the outcome or the event occurred. Women with multiple exposure or unspecific treatment will be specified as "Allocation unknown". Women who stopped their treatment will be assigned to an "Ex-use" cohort.

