#### 5.4.1 Incidence measures

The *incidence rate* (IR) measures the occurrence of new cases per unit of person-time.

$$IR = \frac{Number\ of\ new\ cases}{Total\ follow - up\ time}$$

The incidence rate takes into consideration the patient-specific follow-up time and it assumes a constant hazard rate. For each of n subjects the time  $t_k (k=1,...,K)$  to: (1) the end of the risk period, if recurrent events are allowed or (2) to the first occurrence of a certain event is observed. If the event was not experienced, the (censored) time to the end of the risk period is observed.

In the present study, women-years are conducted as a unit of person-time. Incidence rates are shown per 10^4 women-years (WY) unless otherwise specified.

The *incidence rate ratio* (IRR) is the proportion of two incidence rate estimates.

$$IRR = \frac{Incidence\ rate\ of\ treatment\ group}{Incidence\ rate\ of\ control\ group}$$

Supporting document SOP BMT 01.09 – Doc 5002.02 – Effective date 21.03.2017

The incidence rate ratio gives a measure of how much more likely an event occurs in subjects under exposure (treatment group) than in subjects who were not exposed (control group).

The *incidence proportion* (IP) measures the occurrence of new cases in relation to the size of the population at risk within a given period of time (cumulative incidence).

$$IP = \frac{Number\ of\ new\ cases}{Size\ of\ population\ at\ risk}$$

Exact 95% confidence intervals for prevalence, incidence proportion, incidence rate, and incidence rate ratio will be calculated in accordance with Clopper and Pearson[9].

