#### 6.2 Variable definitions

All time-related variables (age, first diagnosis, first symptoms) are calculated in relation to the study entry date.

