#### Section B **Population Characteristics**

Section B-1 Age and body measurements

Section B-1.1 Age at study entry

Table B-1.1.1 Age (years) at study entry, ITT population, Complete cohort

	DNG	OAED		NAED		Allocation unknown	Total		
		GnRH-a	Danazol	All OAED	CC	Other progestin	All NAED		
Number (%) of women	xx ( 100%)	xx ( 100%)	xx ( 100%)	xx ( 100%)					
Age (years)									
n	xx ( xx.x%)	xx ( xx.x%)	xx ( xx.x%)	xx ( xx.x%)					
Missing	0 ( 0.00%)	0 ( 0.00%)	0 ( 0.00%)	0 ( 0.00%)	0 ( 0.00%)	0 ( 0.00%)	0 ( 0.00%)	0 ( 0.00%)	0 ( 0.00%)
Mean	xx.x	xx.x	xx.x	xx.x	xx.x	xx.x	xx.x	xx.x	XX.X
SD	xx.xx	xx.xx	xx.xx	xx.xx	xx.xx	xx.xx	XX.XX	XX.XX	xx.xx
Min	XX	XX	xx	XX	xx	XX	XX	XX	XX
Q1	XX.X	XX.X	xx.x	XX.X	xx.x	xx.x	xx.x	XX.X	XX.X
Median	XX.X	xx.x	xx.x	xx.x	xx.x	xx.x	xx.x	XX.X	xx.x
Q3	XX.X	XX.X	xx.x	xx.x	xx.x	XX.X	xx.x	XX.X	XX.X
Max	xx	XX	XX	XX	XX	XX	xx	xx	xx
Adolescents <18 years	xx ( xx.x%)	xx ( xx.x%)	xx ( xx.x%)	xx ( xx.x%)					
Age category									
<20 years	xx ( xx.x%)	xx ( xx.x%)	xx ( xx.x%)	xx ( xx.x%)					
20 to <30 years	xx ( xx.x%)	xx ( xx.x%)	xx ( xx.x%)	xx ( xx.x%)					
30 to <40 years	xx ( xx.x%)	xx ( xx.x%)	xx ( xx.x%)	xx ( xx.x%)					
≥40 years	xx ( xx.x%)	xx ( xx.x%)	xx ( xx.x%)	xx ( xx.x%)					
Missing	0 ( 0.00%)	0 ( 0.00%)	0 ( 0.00%)	0 ( 0.00%)	0 ( 0.00%)	0 ( 0.00%)	0 ( 0.00%)	0 ( 0.00%)	0 ( 0.00%)

Table B-1.1.2	Age (years) at study entry, AT population, Complete cohort
Table B-1.1.3	Age (years) at study entry, AT population, Starter
Table B-1.1.4	Age (years) at study entry, AT population, Switcher
Table B-1.1.5	Age (years) at study entry, AT population, Restarter
Table B-1.1.6	Age (years) at study entry, AT population, Diagnosis confirmed by surgery
Table B-1.1.7	Age (years) at study entry, AT population, Diagnosis based on clinical symptoms
Table B-1.1.8	Age (years) at study entry, AT population, Germany
Table B-1.1.9	Age (years) at study entry, AT population, Poland
Table B-1.1.10	Age (years) at study entry, AT population, Hungary
Table B-1.1.11	Age (years) at study entry, AT population, Switzerland
Table B-1.1.12	Age (years) at study entry, AT population, Russia
Table B-1.1.13	Age (years) at study entry, AT population, Ukraine

Supporting document SOP BMT 01.09 – Doc 5002.02 – Effective date 21.03.2017

Section B-1.2 Height (cm) and Weight (kg) at study entry

Table B-1.2.1 Height (cm) and Weight (kg) at study entry, ITT population, Complete cohort

	DNG	OAED			NAED			Allocation unknown	Total

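### The adolescence tables classify women once, at study entry, so their rates mix experience before age 18 with adult experience; an attained-age split should be added

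*SAP*

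**What the plan says.** The SAP's secondary objectives (section 2) include this one: "To investigate the risks of short and long-term use of DNG and of established endometriosis treatments in adolescent women". Section 5.4.4 turns it into anemia and depression in adolescence, and section 8 adds treatment discontinuation.

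The rules that decide whose experience is counted are spread over the SAP:

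- **Age cut-off.** Section 6.2.2 does not define adolescent. The cut-off appears only in the mock tables, as "Adolescents <18 years" in Table B-1.1.1.
- **When age is measured.** Section 6.2: "All time-related variables (age, first diagnosis, first symptoms) are calculated in relation to the study entry date".
- **Who enters the adolescence tables.** Tables C-2.2.1, C-2.3.1 and C-2.4.1 all carry the footnote "Adolescent at study entry".
- **What is counted.** Section 5.4.1 runs person-time to the event or to the end of the risk period; for a woman without the event, "the (censored) time to the end of the risk period is observed". No age limit is set. Section 5.1 allocates by current treatment: "outcomes of interest or adverse events will be assigned to the treatment at the time the outcome or the event occurred". Table C-2.4.1 counts treatment starts and expressly includes later switches and restarts.
- **For how long.** Section 3: "Women will be followed-up for at least 2 years", with a maximum of 7 years for early recruits.

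**The concern.** A girl who enters on her 17th birthday has one year left before she is 18. With 2 years of follow-up, half of her time is adult; with 7 years, six sevenths (86%) is. A restart at age 22 counts in C-2.4.1 as a treatment start for adolescence.

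The objective asks about risk in adolescent women, and C-2.2 and C-2.3 are the only anemia and depression rates planned for it. If risk differs before and after 18, these tables cannot show it. The mixture also need not be the same in every column, because the adult part grows with time on treatment. SAP 5.2 expects dienogest users to stay on treatment longer and gives six months as an example of a fixed GnRH-agonist course. A side-by-side reading of the columns would then partly compare different ages.

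**Working it through.** **The plan's own figure.** The documents give no number of adolescents and no adolescent women-years or events. The one related figure is the total observation time in SAP Table 1, 89,086 women-years. It can be reproduced from 8,334 recruits per year for three years and 10% annual drop-out taken as a constant hazard λ = −ln 0.9 = 0.105. The first year-end count is 8,334 × (1 − 0.9)/0.105 = 7,910, as stated. The total comes to 89,052 (trapezoid rule) or 88,981 (exact integral), within about 0.1%. The drop-out model is therefore adequate for what follows.

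**Adult share of on-treatment time.** With stopping hazard h, let k = λ + h and S(t) = (1 − e^(−kt))/k, the expected on-treatment time within t years. For entry age a and possible follow-up F:

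adult share = 1 − E[S(min(18 − a, F))] / E[S(F)]

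Inputs:

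- F uniform on 2 to 7 years. The limits are from SAP section 3; the uniform shape is an assumption.
- λ = 0.105 (SAP section 4).
- Entry age uniform from a floor up to 18. **Assumption:** the documents give no entry ages, so floors of 12, 14, 15 and 16 were tried.
- h = 2, 1, 0.5 and 0.28 per year, that is, mean use 1/h of 0.5, 1, 2 and 3.6 years. **Assumption.** The last value lies within the plan's 0.25–0.30 for treatment failure (section 4), read as a yearly hazard. Those figures leave out other reasons for stopping, so true use may be shorter.

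One case by hand, floor 16 and h = 1, so k = 1.105. Since 18 − a never exceeds 2 and F is at least 2, the minimum is always 18 − a.

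- Under 18: (1/1.105) × [1 − (1 − e^(−2.211))/2.211] = 0.540 years.
- All on-treatment time: (1/1.105) × [1 − (e^(−2.211) − e^(−7.738))/(5 × 1.105)] = 0.887 years.
- Adult share: 1 − 0.540/0.887 = 39%.

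All cases:

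| Mean use | floor 12 | floor 14 | floor 15 | floor 16 |
|---|---|---|---|---|
| 0.5 years | 8% | 12% | 16% | 23% |
| 1 year | 14% | 21% | 28% | 39% |
| 2 years | 22% | 32% | 41% | 54% |
| 3.6 years | 27% | 39% | 49% | 62% |

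If every woman had only the 2-year minimum, the shares would be lower: 7–22% at 0.5 years of mean use and 11–33% at 1 year. This matters for the comparator. Recruitment was reopened for 2,000 OAED patients (SAP 3.1, footnote 8) from spring 2015 to June 2016 (SAP 3.2), with follow-up to mid-2018, so that wave has only about 2 to 3 years.

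**Difference between columns.** At floor 15, a column with mean use of 3.6 years would be 49% adult and one with six-month courses 16%. This illustrates the direction; it does not predict either column.

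**What the calculation does not cover.** The share of events equals the share of women-years only if the hazard does not change with age. C-2.4.1 is a proportion per treatment start, so the formula does not apply. Every study-entry start there is under 18 by definition; the adult share of later starts is unknown.

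**The case against.** The strongest defence is that this is a disclosed cohort definition that suits part of the objective. The footnote states it, and section 6.2 applies the same convention to age throughout. The objective covers long-term use, which section 6.2.2 sets at 15 months or more of continuous intake. A girl who enters after age 16.75 cannot reach 15 months before she is 18. With entry ages uniform over 15–18 that is 1.25/3 = 42% of entrants, and over 16–18 it is 1.25/2 = 62.5%. Tables limited to time before 18 could not show long-term use for them. This stands, and it is why the entry-defined cohort should be kept.

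The tables are also descriptive. No adolescent hypothesis, model or sample size exists, and Section D compares whole cohorts only. This stands too, and it limits the weight of the point.

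Three stronger readings are tempting, and the documents do not support them:

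- *Most of the adolescent rate is adult.* Half or more is reached in only two of the sixteen cases above, both with the oldest entry floor and long use. Without entry ages the claim cannot be made.
- *Time after stopping dilutes the treatment rates.* Section 5.1 moves women who stop to an Ex-use cohort, and Table C-2.2.1 gives it a separate column. The adult share of all follow-up (37–73% for floors 12–16, from the same formula with h = 0) bears on the Total, not on a DNG, OAED or NAED rate.
- *A doubled adolescent risk would read as 1.6.* That is 0.6 × 2 + 0.4 × 1. It needs a 40% adult share and an excess that vanishes on the 18th birthday. It shows only how dilution works.

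**Conclusion.** The point holds as a matter of construction: tables presented as rates for adolescence pool experience before and after age 18, and nothing in the plan separates the two. That all later time counts follows from the absence of any age-based censoring or splitting rule, not from an explicit sentence.

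The size is conditional. For entry-age floors of 12–16 and 2–7 years of follow-up, the adult share of on-treatment time is about 8–23% with six-month courses and about 14–62% with mean use of 1 to 3.6 years. Entry ages and durations of use are assumptions. The share rises with duration, so it can differ between dienogest and comparator columns. The adult share of treatment starts in C-2.4 is unknown.

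This is a worthwhile, inexpensive improvement to secondary descriptive tables, not a flaw in the primary analysis.

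**What to change.** 1. Define adolescent (under 18) in SAP 6.2.2.
2. Keep the entry-defined cohort and its totals in C-2.2 to C-2.4, and retitle the tables so that the definition at study entry is in the title, not only in the footnote.
3. In C-2.2.1, C-2.3.1 and C-2.4.1, also split women-years, events and treatment starts at the 18th birthday, and show under 18 and 18 or over side by side for each treatment column.

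No new data are needed. Date of birth is question 5 of the baseline questionnaire. The follow-up questionnaire asks for month and year of treatment start and stop, and of anemia and depression diagnoses, so the split is accurate to about a month.

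The cost is one split date per woman and wider intervals for the under-18 rates. The two parts add up to the entry-defined total, so nothing now planned is lost, and no primary hypothesis or sample-size figure changes.

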#### Section C-2.3 Incidence rate of new depression or worsening of existing depression for adolescence

Table C-2.3.1 Incidence rate of new depression or worsening of existing depression for adolescence\*, AT population, Complete cohort

	DNG		OAED			NAED			Allocation unknown	Total
		GnRH-a	Danazol	All OAED	СНС	Other progestin	All NAED			
Number of women years	xx	xx	xx	xx	xx	xx	xx	xx	xx	xx
Confirmed depression	xx	xx	xx	xx	xx	xx	xx	xx	xx	xx
IR** (95% CI) Thereof	xx.x (xx.x-x.x)	xx.x (xx.x–x.x)	xx.x (xx.x-x.x)	xx.x (xx.x-x.x)	xx.x (xx.x–x.x)	xx.x (xx.x-x.x)	xx.x (xx.x–x.x)	xx.x (xx.x–x.x)	xx.x (xx.x–x.x)	xx.x (xx.x-x.x)
Treated by psychiatrist	XX	xx	xx	XX	XX	xx	XX	xx	xx	xx
	xx.x (xx.x-x.x)	xx.x (xx.x-x.x)	xx.x (xx.x-x.x)	xx.x (xx.x-x.x)	xx.x (xx.x–x.x)	xx.x (xx.x-x.x)	xx.x (xx.x-x.x)	xx.x (xx.x-x.x)	xx.x (xx.x-x.x)	xx.x (xx.x-x.x)
Hospital admission	xx	xx	xx	xx	xx	xx	XX	xx	xx	xx
	xx.x (xx.x–x.x)	xx.x (xx.x–x.x)	xx.x (xx.x–x.x)	xx.x (xx.x–x.x)	xx.x (xx.x–x.x)					
Suicide attempt	xx	xx	xx	xx	xx	xx	xx	xx	xx	xx
	xx.x (xx.x-x.x)	xx.x (xx.x–x.x)	xx.x (xx.x–x.x)	xx.x (xx.x–x.x)	xx.x (xx.x–x.x)	xx.x (xx.x–x.x)				
Committed suicide	xx	xx	xx	xx	xx	xx	xx	xx	xx	xx
	xx.x (xx.x-x.x)	xx.x (xx.x–x.x)	xx.x (xx.x–x.x)	xx.x (xx.x–x.x)	xx.x (xx.x–x.x)	xx.x (xx.x–x.x)				
Personal history	xx	xx	xx	xx	xx	xx	xx	xx	xx	xx
of depression	xx.x (xx.x-x.x)	xx.x (xx.x-x.x)	xx.x (xx.x-x.x)	xx.x (xx.x-x.x)	xx.x (xx.x–x.x)	xx.x (xx.x-x.x)	xx.x (xx.x-x.x)	xx.x (xx.x-x.x)	xx.x (xx.x-x.x)	xx.x (xx.x-x.x)
Family history	xx	xx	xx	xx	xx	xx	xx	xx	xx	xx
of depression	xx.x (xx.x-x.x)	xx.x (xx.x-x.x)	xx.x (xx.x–x.x)	xx.x (xx.x–x.x)	xx.x (xx.x–x.x)	xx.x (xx.x-x.x)	xx.x (xx.x-x.x)	xx.x (xx.x-x.x)	xx.x (xx.x-x.x)	xx.x (xx.x–x.x)

Note: \* Adolescent at study entry.

Note: \*\* Incidence rate is shown per 10^4 women years.

Table C-2.3.2	Incidence rate of new depression or worsening of existing depression for adolescence*, AT population, Starter
Table C-2.3.3	Incidence rate of new depression or worsening of existing depression for adolescence*, AT population, Switcher
Table C-2.3.4	Incidence rate of new depression or worsening of existing depression for adolescence*, AT population, Restarter
Table C-2.3.5	Incidence rate of new depression or worsening of existing depression for adolescence*, AT population, Diagnosis confirmed by surgery
Table C-2.3.6	Incidence rate of new depression or worsening of existing depression for adolescence*, AT population, Diagnosis based on clinical symptoms
Table C-2.3.7	Incidence rate of new depression or worsening of existing depression for adolescence*, AT population, Germany
Table C-2.3.8	Incidence rate of new depression or worsening of existing depression for adolescence*, AT population, Poland
Table C-2.3.9	Incidence rate of new depression or worsening of existing depression for adolescence*, AT population, Hungary
Table C-2.3.10	Incidence rate of new depression or worsening of existing depression for adolescence*, AT population, Switzerland
Table C-2.3.11	Incidence rate of new depression or worsening of existing depression for adolescence*, AT population, Russia
Table C-2.3.12	Incidence rate of new depression or worsening of existing depression for adolescence*, AT population, Ukraine

Supporting document SOP BMT 01.09 - Doc 5002.02 - Effective date 21.03.2017

#### Section C-2.4 Incidence proportions of treatment discontinuation for adolescence

Table C-2.4.1 Incidence proportions of treatment discontinuation for adolescence\*, AT population, Complete cohort

	DNG		OAED			NAED	Allocation unknown	Total	
	•	GnRH-a	Danazol	All OAED	СНС	Other progestin	All NAED		
Number of treatment starts	xx	xx	xx	xx	xx	xx	xx	xx	xx
Treatment failure	xx	xx	xx	xx	xx	xx	xx	xx	xx
IP** (95% CI) Thereof***	xx.x (xx.x–x.x)	xx.x (xx.x–x.x)	xx.x (xx.x–x.x)	xx.x (xx.x-x.x)	xx.x (xx.x–x.x)	xx.x (xx.x–x.x)	xx.x (xx.x–x.x)	xx.x (xx.x–x.x)	xx.x (xx.x-x.x)
Medication ineffective	xx	xx	xx	xx	xx	xx	xx	xx	xx
	xx.x (xx.x–x.x)	xx.x (xx.x-x.x)	xx.x (xx.x-x.x)	xx.x (xx.x–x.x)	xx.x (xx.x-x.x)				
Side effects	xx	xx	xx	xx	xx	xx	xx	xx	xx
	xx.x (xx.x–x.x)	xx.x (xx.x-x.x)	xx.x (xx.x-x.x)	xx.x (xx.x–x.x)	xx.x (xx.x-x.x)				

Note: \* Adolescent at study entry

Note: \*\* Incidence proportion is shown per 102 treatment starts, including incident exposure at study entry, switches between exposure groups and/or restarts within exposure groups.

Note: \*\*\* Multiple answers possible.

Table C-2.4.2	Incidence proportions of treatment discontinuation for adolescence*, AT population, Starter
Table C-2.4.3	Incidence proportions of treatment discontinuation for adolescence*, AT population, Switcher
Table C-2.4.4	Incidence proportions of treatment discontinuation for adolescence*, AT population, Restarter
Table C-2.4.5	Incidence proportions of treatment discontinuation for adolescence*, AT population, Diagnosis confirmed by surgery
Table C-2.4.6	Incidence proportions of treatment discontinuation for adolescence*, AT population, Diagnosis based on clinical symptoms
Table C-2.4.7	Incidence proportions of treatment discontinuation for adolescence*, AT population, Germany
Table C-2.4.8	Incidence proportions of treatment discontinuation for adolescence*, AT population, Poland
Table C-2.4.9	Incidence proportions of treatment discontinuation for adolescence*, AT population, Hungary
Table C-2.4.10	Incidence proportions of treatment discontinuation for adolescence*, AT population, Switzerland
Table C-2.4.11	Incidence proportions of treatment discontinuation for adolescence*, AT population, Russia
Table C-2.4.12	Incidence proportions of treatment discontinuation for adolescence*, AT population, Ukraine

Table C-2.6.8

